2. Endpoints for Acceptability: We will judge acceptability by participant ratings, and by actual program usage data. Participants will rate the Intervention at follow-up. The range of items on this scale is from 1 to 7. An item mean of 3.5 would be mid-range. Basic descriptive information will be gathered from the tracking system about whether participants logged in, how many times, and for how long. Time spent in each Core will be tracked and summarized. We will judge *eHealth Positive* acceptable if if the average score on the evaluation was ≥ 5.6 , which is 80% of the highest score (range 1-7), and if 75% of participants completed at least half of the Cores and provide 4 of 7 daily diaries of adherence on at least 4 weeks.

Pilot RCT of Patient Centered eHealth Intervention for Nonadherent HIV+ Substance Users. NCT Unique protocol ID 18938. Document Date Oct 31, 2022

3. Endpoints for preliminary efficacy components: PRIMARY: HIV viral suppression rates for the experimental vs. control group SECONDARY: adherence (6M average pharmacy refill rate), retention in care (6M missed visit proportion), and substance using days per 30 day period. Because this is a pilot study, we are not estimating power and precision, but rather, gathering information on effect size to assist in estimating power for a subsequent definitive trial.

Pilot Study, no early stopping, no interim analyses, no stratification.

3. Provide a justification for the sample size used in this protocol.

Because this is a pilot study, we are not estimating power and precision, but rather, gathering information on effect size to assist in estimating power for a subsequent definitive trial. Rather, in our experience with pilot trials of behavioral interventions, and of Internet interventions, an n of 25 per group is usually sufficient for detecting a signal and for estimating effect size. As detailed above, we may consent 100 participants to get 71 fully enrolled and an n of 50 (25 per group) with all data available for analysis.

4. What is your plan for primary variable analysis?

Primary research questions and analytic approach:

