Basic descriptive information will be gathered from the tracking system about whether participants logged in, how many times, and for how long. Time spent in each Core will be tracked and summarized. We will judge *eHealth Positive* acceptable if if the average score on the evaluation was ≥ 5.6 , which is 80% of the highest score (range 1-7), and if 75% of participants completed at least half of the Cores and provide 4 of 7 daily diaries of adherence on at least 4 weeks.

- 3. Does eHealth Positive show promise, showing impact on knowledge and usage of coping strategies? Preliminary efficacy.** To assess the promise of Pos4Health, we will test it in a pilot RCT among 50 nonadherent PLWH recruited from throughout the South, Virginia, and the United States--particularly areas with rural and nonurban occupants. The study will compare Pos4Health to a static Patient Education website for its impact on the primary outcome of viral suppression rate. Additionally, to inform a subsequent RCT, we will record the impact on secondary outcome variables of adherence (6M average pharmacy refill rate), retention in care (6M missed visit proportion), and on substance using days per 30 day period. The pilot test will also provide data on varied types of substance users, allowing some basic comparisons between non-injection and injection drug users, or between drinkers and drug users. While this pilot study will not be powered for direct statistical comparisons, we will examine the data for each primary and secondary outcome by these groups. If the data indicate potential differences, we will examine these in simple regression analyses. Data will be collected in person and through the web program, and electronically from the electronic medical records of clinics and pharmacies. We will characterize the data using standard methods (means, medians, standard deviations, confidence intervals). Prior to analyses, psychometric analyses will be conducted to assess reliability of the measures and to adjust for abnormal distributions. We will also characterize patterns of missing data. Paired t- tests will compare change over time from baseline to post-treatment follow-up. We anticipate the use of nonparametric tests to allow for non-normality. Linear regression models will be used to adjust for effects of relevant covariates on participant responses over time. We will assess the magnitude of associations among the outcome variables using Pearson's correlation coefficients.

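### User-type regressions are fitted only where the same data already suggest a difference, by an undefined criterion, so the modelled estimates are biased away from zero

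*SAP*

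**What the plan says.** Question 4, item 3 of the SAP (preliminary efficacy) notes that the sample will be mixed in its substance use and describes this as "allowing some basic comparisons between non-injection and injection drug users, or between drinkers and drug users". A caveat on sample size comes next: "While this pilot study will not be powered for direct statistical comparisons". Despite that caveat, every outcome is to be looked at by user type, in these words: "we will examine the data for each primary and secondary outcome by these groups". The step to modelling is then made conditional: "If the data indicate potential differences, we will examine these in simple regression analyses".

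The outcomes are listed in question 2, item 3. The primary one is "PRIMARY: HIV viral suppression rates for the experimental vs. control group". The secondary ones are "adherence (6M average pharmacy refill rate), retention in care (6M missed visit proportion), and substance using days per 30 day period". The sample size answer (question 3) expects "an n of 50 (25 per group) with all data available for analysis", and question 2 states "Pilot Study, no early stopping, no interim analyses, no stratification", so the sizes of the user-type groups are left to recruitment.

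The SAP gives no threshold, test or effect size that would make a difference a potential one. It does not list the terms of these regressions and has no rule for reporting them.

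**The concern.** The look that decides whether a contrast is modelled uses the same outcome data as the model. A contrast passes because its observed difference is large, and part of any large observed difference in a sample of 50 is sampling error. Conditional on passing, the estimate is too far from zero on average. The usual 95% interval and p-value take no account of the selection. This holds whether the true difference is zero or modest, and the exaggeration is greatest when groups are small.

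This matters here because the SAP names effect sizes as what the pilot is to deliver: questions 2, 3 and 5 all say that they will feed the planning of the later trial. A user-type effect taken from a triggered regression would be the kind of figure that the selection inflates. Because the trigger is undefined, nobody could work out afterwards how strong the selection was.

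**Working it through.** The SAP gives no alpha, power or effect size for these comparisons, so there is no figure of its own to reproduce. The size of the problem can only be illustrated.

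**Inputs from the SAP**
- Contrasts: 2 (non-injection vs injection drug users; drinkers vs drug users).
- Outcomes: 1 primary + 3 secondary = 4, so 2 × 4 = 8 possible contrasts.
- Analysed participants: 50.

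**Assumptions not in the SAP**
- No true difference between user types.
- Each contrast divides all 50 people, with the smaller group 20% to 50% of them (10/40 to 25/25).
- Outcomes are continuous with SD 1 and mutual correlation 0 to 0.6.
- Two-sided 5% level.
- The undefined criterion is represented by an observed standardised difference |d| above 0.5, with 0.3 as a second case.

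**Step 1. Standard error of a group difference:** SE = √(1/n₁ + 1/n₂).
- 25/25: √(0.04 + 0.04) = 0.283 SD.
- 10/40: √(0.10 + 0.025) = 0.354 SD.

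**Step 2. Chance that one null contrast passes a 0.5 SD trigger:** P(|t| > 0.5/SE), 48 degrees of freedom.
- 25/25: 0.5/0.283 = 1.77, P = 0.083.
- 10/40: 0.5/0.354 = 1.41, P = 0.164.

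**Step 3. Share of triggered null contrasts with p<0.05.** Nominal significance needs |d| above 0.57 (25/25) or 0.71 (10/40). Both exceed 0.5, so every significant contrast has also passed the trigger, and the share is 0.05/P.
- 25/25: 0.05/0.083 = 60%.
- 10/40: 0.05/0.164 = 31%.

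**Step 4. Mean |d| among triggered null contrasts:** SE × E(t | t > 0.5/SE).
- 25/25: 0.62 SD.
- 10/40: 0.67 SD.

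**Step 5. Simulation.** 20,000 null pilots of 50 were run for each combination of split and correlation.

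| Trigger | At least one of eight passes | Mean abs(d) if triggered | p<0.05 if triggered |
|---|---|---|---|
| 0.3 SD | 88% to 98% | 0.45 to 0.50 SD | 12% to 17% |
| 0.5 SD | 40% to 76% | 0.62 to 0.67 SD | 30% to 60% |

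The simulation agrees with steps 2 to 4. A stricter trigger sends fewer contrasts to regression but exaggerates those that pass by more.

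**Limits.** The primary outcome is binary, so the SD scale is only a guide for it. The injection contrast applies to drug users alone and would involve fewer than 50 people if drinkers form a separate group. Its SE, and the chance exaggeration, would then be larger than shown.

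**The case against.** The best defence is that this is a pilot focused on feasibility and acceptability. The SAP calls the comparisons basic, says outright that they are not powered, and rests no go/no-go rule on them. That stands, and it keeps the point minor. It does not answer it, though: a statement about power warns of missed effects, whereas selection on size overstates the effects that are found, and small groups make this worse.

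Several stronger readings are tempting, and the SAP does not support them.
- *Untriggered contrasts go unreported.* Every outcome is to be examined by group, and the same paragraph promises means, medians, standard deviations and confidence intervals. Only the regression is conditional. There is no reporting rule in either direction.
- *The contrasts are selected purely by chance.* A real difference would also trigger a regression. The selection is on observed size, which mixes signal and error.
- *The results decide whom the next trial targets.* The stated use is effect size for planning, and no text links user type to the later trial's population.
- *The regressions ignore arm.* The terms are not listed, and the SAP poses no question about treatment effect by user type. A missing arm term is an inference from silence.
- *The chance of a false finding across eight tests measures the bias.* For independent tests, 1 − 0.95⁸ = 34%. That is multiplicity. It would be the same if all eight contrasts were fitted, so it does not measure the effect of the trigger.

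Requiring an arm-by-user-type logistic model for suppression would also be open to objection. Assume 5 people per arm in the smaller user group. At 50% suppression, a cell is all suppressed or all unsuppressed with probability 2 × 0.5⁵ = 0.0625, so at least one of the two cells is with probability 1 − 0.9375² = 12%. At 70% the figures are 0.7⁵ + 0.3⁵ = 0.1705 and 1 − 0.8295² = 31%. The interaction estimate is then not finite.

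**Conclusion.** The concern holds in a limited form. The SAP makes the user-type regressions conditional on an undefined look at the same data, so what is modelled is chosen on its observed size and is biased away from zero. With no true differences and a 0.5 SD trigger, triggered contrasts average about 0.62 to 0.67 SD and about 30% to 60% reach p<0.05. With a 0.3 SD trigger the figures are about 0.45 to 0.50 SD and 12% to 17%. These rest on the assumed triggers, splits and correlations set out above; the SAP fixes none of them, so they show the order of magnitude and do not predict this trial's results. The effect on the pilot's main conclusions is small, because feasibility, acceptability and the comparison of arms do not depend on these regressions.

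**What to change.** Delete the conditional sentence in question 4, item 3, and replace it with a fixed rule:

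- For both user-type contrasts on all four outcomes, report the between-group estimate adjusted for arm, and for the baseline value where collected, with a 95% confidence interval, whatever the data show.
- Fix the scale of the suppression estimate in advance.
- Label all eight as exploratory and make no significance statements. Reporting all eight removes the selection on size but does not lower the chance that one of them crosses 5%, so the second half of this rule is needed too.
- If treatment effect by user type is of interest, describe the arm difference within each user type with its interval. Do not require an interaction model, which may not be estimable for suppression with 50 people.

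The cost is SAP wording and a few more model fits. The downside is that the intervals will be visibly wide. For a continuous outcome, before any gain from baseline adjustment, the half-width is about 2.01 × 0.283 = 0.57 SD at 25/25 and 2.01 × 0.354 = 0.71 SD at 10/40. That is a fair picture of what 50 participants can say about user types.
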